5.2. Primary Outcome

• Treatment success rate at 24 months after the initiation of treatment:

- ‘Cured’ and ‘treatment completed’ are defined as treatment success, and ‘culture’ defined below refers to results of liquid culture.
- Treatment failure, death, loss to follow-up, transfer out and relapse were excluded from treatment success.
- Definitions of treatment outcomes refer to 2014 WHO Guidelines (20). However, ‘stopping’ of drugs during treatment will not be considered as ‘drug change’ (Please see ‘6 Definitions’ in this protocol below.).

5.3. Secondary Outcomes

- Time to sputum *Mycobacterium tuberculosis* (MTB) culture conversion to negative (liquid and solid culture media)
- Sputum MTB culture conversion proportion at two months of treatment (liquid and solid culture media)
- Sputum MTB culture conversion proportion at six months of treatment (liquid and solid culture media)
- AE of grade 3 and higher
- Proportion of participants with a treatment success at the end of treatment.
- Proportion of relapse after treatment success (investigational arm)
- Proportion of death and time-to-death
- Comparison of treatment success rates between treatment groups according to pyrazinamide resistance.

5.4. Inclusion Criteria

- 1) Men and women age ≥ 19 and ≤ 85
- 2) Confirmed pulmonary MDR-TB by phenotypic or genotypic drug susceptibility tests or RR-TB by genotypic tests such as Xpert® MTB/RIF assay regardless of being positive for sputum acid-fast bacilli smear
- 3) Use of current anti-TB regimen with second-line drugs for ≤ 14 days at the time of enrollment

5.5. Exclusion Criteria

- 1) Known any fluoroquinolone-resistant MDR-TB patients
- 2) Known XDR-TB patients
- 3) Patients who are pregnant or who are unwilling to use proper contraceptives at childbearing age
- 4) Medical history of galactose intolerance, Lapp lactase deficiency, glucose-galactose

Confidential

MDR-END v14.0, 20Mar2020

malabsorption

- 5) The need for ongoing use of prohibited drugs while on study drugs
- 6) History of optic neuropathy or peripheral neuropathy
- 7) People with any of the following test results
 - i. Absolute neutrophil count $< 2000 / \mu\text{L}$
 - ii. White blood cell count (WBC) $< 3.0 \times 10^3 / \mu\text{L}$
 - iii. Hemoglobin $< 7.0 \text{ g/dL}$
 - iv. Serum creatinine $> 2.0 \text{ mg/dL}$
 - v. Aspartate aminotransferase (AST or SGOT) $> 100 \text{ IU/L}$
 - vi. Alanine aminotransferase (ALT or SGPT) $> 100 \text{ IU/L}$
 - vii. Total bilirubin $> 2.0 \text{ mg/dL}$
 - viii. Albumin $< 2.8 \text{ g/dL}$
 - ix. QTcF $> 500 \text{ ms}$
- 8) History of hypersensitivity reaction to the study drugs

5.6. Precautions for Use and Expected Adverse Events (AE)

5.6.1. Prohibited medications while on the study drugs

- MAOIs (phenelzine, isocarboxazid, selegiline, and moclobemide)
- Strong CYP3A inducer (i.e.; carbamazepine)

5.6.2. Warning and precautions against using simultaneously

① Delamanid

- Drugs listed below that may expand QT intervals
 - i. Antiarrhythmic drugs (amiodarone, disopyramide, dofetilide, ibutilide, procainamide, quinidine, hydroquinidine, sotalol)
 - ii. Neuroleptics (phenothiazine, sertindole, sultopride, chlorpromazine, haloperidol, mesoridazine, pimozide, thioridazine), antidepressants
 - iii. Antimicrobials: Macrolides (erythromycin, clarithromycin), moxifloxacin, sparfloxacin, Bedaquiline, Triazole antifungal agents, Pentamidine, Saquinavir

- iv. Non-sedating antihistamine agents (terfenadine, astemizole, mizolastine)
- v. Cisapride, droperidol, domperidone, bepridil, probucol, levomethadyl, methadone, vinca alkaloids, arsenic trioxide
- Strong inhibitors of CYP3A: Increases delamanid metabolites in blood (approximately 30%)
- When having medical history related to the following heart abnormality
 - i. QTc prolongation (> 450ms for males, and >470ms for females)
 - ii. History of symptomatic arrhythmia, or taking anti-arrhythmic agents
 - iii. Alleged severe hypertension, left ventricular hypertrophy, or congenital heart disease with decreased ejection fraction of left ventricle
- Breastfeeding patient: It is recommended that women should not breastfeed during treatment

② Linezolid

- When there is possibility of causing serotonin syndrome
 - i. Patients with carcinoid syndrome
 - ii. Selective Serotonin reuptake inhibitors (SSRI), tricyclic antidepressants, serotonin 5-HT1 receptor agonists (triptans), meperidine, bupropion, or buspirone
- When requiring blood pressure monitoring
 - i. Uncontrolled hypertension, pheochromocytoma, thyrotoxicosis
 - ii. Administer together with sympathomimetic agents (e.g., pseudoephedrine), vasopressive agents (e.g., epinephrine, norepinephrine), dopaminergic agents (e.g., dopamine, dobutamine)
- Blood glucose monitoring of diabetic patients: Precaution for possibility of hypoglycemia

5.6.3. Expected Adverse Events (AE)

- The subjects will be monitored for AEs of delamanid and linezolid treatments by the primary medical team at each site. The expected major AEs are as follows.

① Delamanid

System Organ Class	Frequency uncommon	Frequency common	Frequency very common
Infections and infestations	Herpes zoster Oropharyngeal candidiasis Tinea versicolor*		
Blood and lymphatic system	Leukopenia Thrombocytopaenia	Anemia* Eosinophilia*	Reticulocytosis

disorders			
Metabolism and nutrition disorders	Dehydration Hypocalcemia Hypercholesterolemia	Hypertriglyceridemia	Hypokalemia Decreased appetite Hyperuricemia*
Psychiatric disorders	Aggression Delusional disorder, persecutory type Panic disorder Adjustment disorder with depressed mood Neurosis Dysphoria Mental disorder Sleep disorder Libido increased*	Psychotic disorder Agitation Anxiety and anxiety disorder Depression and depressed mood Restlessness	Insomnia
Nervous system disorders	Lethargy Balance disorder Radicular pain Poor quality sleep	Neuropathy peripheral Somnolence* Hypoesthesia	Dizziness* Headache Paresthesia Tremor
Eye disorders	Conjunctivitis allergic*	Dry eye* Photophobia	
Ear and labyrinth disorders		Ear pain	Tinnitus
Cardiac disorders	Atrioventricular block first degree Ventricular extrasystoles* Supraventricular extrasystoles		Palpitations
Vascular disorders		Hypertension Hypotension Hematoma* Hot flush*	
Respiratory, thoracic and mediastinal disorders		Dyspnea Cough Oropharyngeal pain Throat irritation Dry throat* Rhinorrhea*	Hemoptysis
Gastrointestinal disorders	Dysphagia Paraesthesia oral Abdominal tenderness*	Gastritis* Constipation* Abdominal pain Abdominal pain (lower) Dyspepsia Abdominal discomfort	Vomiting Diarrhoea* Nausea Abdominal pain (upper)
Hepatobiliary disorders	Hepatic function abnormal		
Skin and subcutaneous tissue disorders	Alopecia* Eosinophilic pustular folliculitis* Pruritus generalized* Rash erythematous	Dermatitis Urticaria Rash pruritic* Pruritus* Rash maculo-papular* Rash* Acne Hyperhidrosis	
Musculoskeletal and connective tissue disorders		Osteochondrosis Muscular weakness Musculoskeletal pain* Flank pain Pain in extremity	Arthralgia* Myalgia*
Renal and urinary disorders	Urinary retention Dysuria* Nocturia	Hematuria*	
General	Feeling hot	Pyrexia*	Asthenia

disorders and administration site conditions		Chest pain Malaise Chest discomfort* Oedema peripheral*	
Investigations	Electrocardiogram ST - segment depression Transaminases increased* Activated partial thromboplastin time prolonged* Gamma-glutamyltransferase increased* Blood cortisol decreased Blood pressure increased	Blood cortisol increased	Electrocardiogram QT prolonged

* The frequency for these events was lower for the combined Deltyba plus OBR group in comparison to the placebo plus OBR group.

② Linezolid

The most common adverse events include diarrhea (2.8%-11.0%), headache (0.5%-11.3%), vomiting (3.4%-9.6%), and

- Systemic: headaches, moniliasis, fungal infection, fever
- Mental & Nervous system: dizziness, insomnia
- Special organs: taste alteration
- Digestive system: diarrhea, nausea, vomiting, abdominal pains, abdominal clamping, abdominal distension, constipation, dyspepsia, tongue discoloration and teeth discoloration
- Cardiovascular system: hypertension
- Blood/Lymphatic system: thrombocytopenia, low hemoglobin level, leukopenia, neutropenia
- Urogenital system: vaginal moniliasis
- Skin: rash, pruritus
- Investigation: abnormal blood tests and abnormal liver function tests

6. Definition

6.1. Culture Conversion to Negative

- i. Culture is considered to have converted to negative when two consecutive cultures, taken at least 4 weeks apart, are found to be negative.
- ii. When a subject cannot produce sputum after the first culture negative sputum, that is also defined as culture conversion.
- iii. Encourage to expectorate sputum as much as possible (including induced sputum), but if the subject cannot produce sputum, it will not be deemed as protocol violation.

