6.2. Date of Culture Conversion

For both the above i and ii, the date of culture conversion is defined as the date of the initial negative culture.

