6.3. Reversion

When *Mycobacterium tuberculosis* (MTB) is cultured at least two or more times after negative conversion.

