Conversion (to negative): culture is considered to have converted to negative when two consecutive cultures, taken at least 30 days* apart, are found to be negative. In such a case, the specimen collection date of the first negative culture is used as the date of conversion. (*According to intervals of research visits, it will be 4 weeks)

Reversion (to positive): culture is considered to have reverted to positive when, after an initial conversion, two consecutive cultures, taken at least 30 days* apart, are found to be positive. For the purpose of defining Treatment failure, reversion is considered only when it occurs in the continuation phase. (*According to intervals of research visits, it will be 4 weeks)

7. Study Timeline

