3.6.2 Secondary Efficacy Evaluation

- ① Time to sputum culture conversion¹ after the initiation of treatment (liquid and solid culture media)
- ② Sputum culture conversion proportion at two months of treatment (liquid and solid culture media)
- ③ Sputum culture conversion proportion at six months of treatment (liquid and solid culture media)

¹ The definition of 'culture conversion to negative' is per the protocol section '6. Definition'. Contamination after the first negative culture also corresponds to the 'culture conversion' because *Mycobacterium tuberculosis* was not cultured based on the section 6.1 ① in the protocol.

- ④ Proportion of treatment success at the end of treatment
- ⑤ Proportion of relapse after treatment success
- ⑥ Proportion of death and time-to-death
- ⑦ Primary outcome evaluation between treatment groups according to pyrazinamide resistance

The secondary outcomes are analyzed as following and describe at exploratory levels.

1) Time To Sputum Culture Conversion After the initiation of treatment (Liquid and Solid Culture Media)

- In order to test whether the time to sputum culture conversion after initiation of treatment of the control arm and investigational arm (liquid and solid culture media) are different statistically, the median time is estimated in each group using the Kaplan-Meier method, and the difference of the distribution of time to culture conversion of the two arms is compared using the log-rank test.

2) Sputum Culture Conversion Proportion at Two Months of Treatment (Liquid and Solid Culture Media)

- In order to test whether there is a statistical difference in sputum culture conversion proportions at two months of the treatment between the control arm and the investigational arm (liquid and solid culture media), each arm is summarized by conversion frequency and proportion, and the proportion of sputum culture conversion at two months between the two arms are compared using the Chi-square test and Fisher's exact test.

3) Sputum Culture Conversion Proportion at Six Months of Treatment (Liquid and Solid Culture Media)

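### One negative culture followed by a missing or contaminated sample can count as culture conversion even when later cultures grow MTB, and protocol 6.1 and 6.4 note b disagree on this

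*Combined protocol and SAP*

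**What the plan says.** Protocol 6.1 gives two routes to conversion. The first is "Culture is considered to have converted to negative when two consecutive cultures, taken at least 4 weeks apart, are found to be negative". The second is "When a subject cannot produce sputum after the first culture negative sputum, that is also defined as culture conversion". It does not say how many samples must be missing, over what interval, or whether the inability has to persist. On timing, 6.2 states: "For both the above i and ii, the date of culture conversion is defined as the date of the initial negative culture".

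Later positives are handled only as reversion. Section 6.3 defines it as MTB that "is cultured at least two or more times after negative conversion"; note b to 6.4 requires that "after an initial conversion, two consecutive cultures, taken at least 30 days* apart, are found to be positive". Its stated use is limited: "For the purpose of defining Treatment failure, reversion is considered only when it occurs in the continuation phase". Neither passage says that a conversion, or its date, is withdrawn.

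Note b also defines conversion again: "culture is considered to have converted to negative when two consecutive cultures, taken at least 30 days* apart, are found to be negative" (the asterisk sets the interval to 4 weeks). It has no route for absent sputum.

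For the secondary outcomes, SAP 3.6.2 footnote 1 says: "The definition of 'culture conversion to negative' is per the protocol section '6. Definition". It adds that contamination after the first negative also counts, because MTB did not grow, and cites the first item of 6.1. Neither the footnote nor SAP 5.2.1 to 5.2.3 says what happens when a later culture is positive.

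**The concern.** Time to conversion and the conversion proportions at two and six months are three listed secondary outcomes, each reported on solid and liquid media and compared between arms by log-rank, chi-square or Fisher's test. As written, one negative result and one uninformative sample are enough for an event dated to the negative. If sputum is produced again and grows MTB, the event stays in the data.

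The early visits add to this. A negative at week 1 or week 2 cannot form a qualifying pair with the next scheduled visit, which is less than 4 weeks later. It can be credited under 6.1(ii) if that next visit is dry.

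Because section 6 contains two definitions, the programmer must also choose between them, in an open-label trial whose SAP aims to prevent unplanned analysis. Conversion status is used elsewhere too: it sets the 40- or 52-week duration in the investigational arm (protocol 5.1.2), and lack of conversion is one ground for Treatment failed (6.4).

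**Working it through.** **Step 1. The definitions applied to the same records.** Here 6.1(ii) is read as met by one dry visit. W = week.

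| Record | 6.1(ii) with 6.2, or SAP footnote 1 | 6.1(i) and 6.4 note b | Reversion after the W4 date? |
|---|---|---|---|
| A: W4 negative, W8 no sputum, W12 and W16 positive, W20 and W24 negative | W4 | W20 | Yes, under 6.3 and note b |
| B: W4 negative, W8 no sputum, W12 positive, W16 and W20 negative | W4 | W16 | No: only one positive |
| C: W4 negative, W8 contaminated, W12 positive, W16 and W20 negative | W4 | W16 | No: only one positive |
| D: W4 negative, no sputum at any later visit | W4 | never | No |

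In A the dates differ by 20 − 4 = 16 weeks, and the participant is a two-month converter under one definition only. The reversion in A is complete by W16. That is inside the intensive phase in both arms (6 months investigational; a recommended minimum of 8 months control), so it does not count toward Treatment failed. In B and C reversion is not met at all.

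**Step 2. Size.** The plan has no figure for these outcomes to reproduce; its sample size concerns the primary outcome only. The documents give no rate of isolated negatives or dry visits, so both are assumptions. Let f be the chance that a culture from a participant who never converts is negative, and s the chance of no sputum at a visit, independent of each other. Visits are W1, 2, 4, 8, 12 and so on (protocol 8.4). I take f = 0.10 and s = 0.10 to 0.30.

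- *Credit under 6.1(ii) by W8.* Four visits (W1, 2, 4, 8), each negative and then dry: 4·f(1−s)·s. At s = 0.10: 4 × 0.10 × 0.90 × 0.10 = 3.6%. At s = 0.30: 4 × 0.10 × 0.70 × 0.30 = 8.4%.
- *Credit from two negatives at adjacent visits.* Two pairs (W4–W8, W8–W12): 2·[f(1−s)]². At s = 0.10: 2 × 0.09² = 1.6%. At s = 0.30: 2 × 0.07² = 1.0%.
- *Both routes.* 3.6 + 1.6 = 5.2% and 8.4 + 1.0 = 9.4%. Simulation, which removes double counting, gives 5.1% and 9.0%.
- *Two negatives only, allowing a pair to span dry visits.* 2f²(1−s) + f²(1−s)s + f²(1−s)s². At s = 0.10: 1.80 + 0.09 + 0.01 = 1.9%. At s = 0.30: 1.40 + 0.21 + 0.06 = 1.7%. Simulation gives 1.6–1.8%.
- *Rule proposed below.* The single negative counts only if the next culture obtained is also negative: 4f(1−s)s·f plus the adjacent pairs. At s = 0.10: 0.36 + 1.62 = 2.0%. At s = 0.30: 0.84 + 0.98 = 1.8%. This is back at the two-negative level.

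By W24, simulation gives 11–18% under both routes against 4–5% under two negatives.

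**Step 3. Sensitivity to the assumptions (by W8, simulation).** With f = 0.05 the credit is about 2–4%. With f = 0.20 it is about 12–19%, against 6–7% for two negatives. If two consecutive dry visits are needed (f = 0.10), it falls to about 2–4%. If dryness must last to W28, there is no excess.

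These figures are for participants who never convert. In a whole arm with f = 0.10, s = 0.20 and an assumed median true conversion time of 6 to 10 weeks, the week-8 proportion rises by about 2 to 3 points.

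**The case against.** The best reply is that 6.1(ii) is meant for people who stop producing sputum for good. It speaks of being unable, not of a missed sample, and the next item asks for sputum to be encouraged, including by induction. On that reading records A and B are not 6.1(ii) cases and the week-8 excess disappears. This is a fair reading and it may be the intended one, but the text does not state it. It also cannot cover record C: a contaminated culture says nothing about lasting dryness, and the SAP credits it anyway.

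Second, the plan does not ignore later positives: reversion is a defined event, and a conversion under 6.1(i) is not cancelled by it either. That is true. The difference is that 6.1(i) rests on two documented negatives and the other routes on one. A single later positive does not reach the reversion definition at all.

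Third, the SAP footnote leans on 6.1, and note b presents its terms as those used in the outcome table. This weakens the clash for the secondary outcomes, but the footnote still adopts section 6 without choosing between the two definitions.

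Fourth, these outcomes are described at exploratory level and the rule is the same in both arms. That limits the importance of the point.

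A reader might go further and infer that unconverted participants will enter as early converters, or that the arm difference is shrunk. The documents support neither. The first requires sputum to return and grow MTB, and a loose reading of 6.1(ii) or a contaminated culture. The second needs rates by arm, which are not given.

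**Conclusion.** The point holds as a gap in definition. A participant who has not converted *can* be recorded as an early converter, because the routes that rest on one negative have no persistence requirement and nothing connects a later positive to the conversion outcomes. Separately, 6.1 and 6.4 note b can give different status and dates for one record, as D shows even when the dryness is permanent.

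The 5–9% against about 2% rests on assumed rates, on independence between visits, and on one dry visit being enough; it indicates scale and is not an estimate for this trial. Distortion of the primary outcome has not been shown: the Treatment failed definition uses note b, which needs two negatives. The passages that depend on conversion status nevertheless need one agreed meaning. This should be settled before analysis, but it does not threaten the trial's main conclusion.

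**What to change.** In SAP 3.6.2 footnote 1, for the secondary conversion outcomes only, state that a single negative followed by no sputum or by a contaminated culture counts as conversion only if the next evaluable culture is not positive for MTB. If it is positive, that negative is set aside and conversion is dated from the next qualifying negative. A participant with no further evaluable culture keeps the credit, which preserves the evident purpose of 6.1(ii).

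Add a sensitivity analysis of the same outcomes that counts only two documented negatives.

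The sponsor should reconcile protocol 6.1, 6.3 and 6.4 note b with the places that use conversion status, namely investigational-arm duration and Treatment failed. No clinical rule is proposed here.

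The cost is a few sentences in the SAP and a few lines of programming, with no new data. Conversion proportions become slightly lower. A participant who is dry for a long time and whose first later culture is positive would lose the early date, so such cases should be listed.

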6.2. Date of Culture Conversion

For both the above i and ii, the date of culture conversion is defined as the date of the initial negative culture.

6.3. Reversion

When *Mycobacterium tuberculosis* (MTB) is cultured at least two or more times after negative conversion.

6.4. Treatment Outcome Definitions

Definitions of treatment outcomes refer to 2014 WHO Guidelines (20). For investigational group, 6 months will be considered as intensive phase.

<Definitions of treatment outcomes for drug-resistant patients>

TREATMENT OUTCOME	DEFINITION
Cured	Treatment completed as recommended by the national policy without evidence of failure AND three or more consecutive cultures taken at least 30 days apart are negative after the intensive phase. ^a
Treatment completed	Treatment completed as recommended by the national policy without evidence of failure BUT no record that three or more consecutive cultures taken at least 30 days apart are negative after the intensive phase. ^a
Treatment failed	Treatment terminated or need for permanent regimen change of at least two anti-TB drugs because of: 
•Lack of conversion^b by the end of the intensive phase^a; or•Bacteriological reversion^b in the continuation phase after conversion^b to negative; or•Evidence of additional acquired resistance to fluoroquinolones or second-line injectable drugs; or•Adverse drug reactions.

Died	A patient who dies for any reason during the course of treatment.
Lost to follow-up	A patient whose treatment was interrupted for two consecutive months or more.
Not evaluated	A patient for whom no treatment outcome is assigned. (This includes cases “transferred out” to another treatment unit and whose treatment outcome is unknown).
Treatment success	The sum of Cured and Treatment completed.

^a For Treatment failed, lack of conversion by the end of the intensive phase[†] implies that the patient does not convert within the maximum duration of the intensive phase[†] applied by the programme. If no maximum duration is defined, an 8-month cut-off is proposed. For regimens without a clear distinction between intensive and continuation phases, a cut-off eight months after the start of treatment is suggested to determine when the criteria for Cured, Treatment completed and Treatment failed start to apply. (†For investigational group, 6 months will be considered as intensive phase.)

^b The terms “conversion” and “reversion” of culture as used here are defined as follows :
Conversion (to negative): culture is considered to have converted to negative when two consecutive cultures, taken at least 30 days* apart, are found to be negative. In such a case, the specimen collection date of the first negative culture is used as the date of conversion. (*According to intervals of research visits, it will be 4 weeks)

Reversion (to positive): culture is considered to have reverted to positive when, after an initial conversion, two consecutive cultures, taken at least 30 days* apart, are found to be positive. For the purpose of defining Treatment failure, reversion is considered only when it occurs in the continuation phase. (*According to intervals of research visits, it will be 4 weeks)

7. Study Timeline

